# 8.6. Data Management

This study will use data in the Medicare Database. The Medicare database is de-identified and HIPAA compliant.

# 8.7. Data Analysis

When performing descriptive analysis of continuous data, means, medians, and standard deviations will be provided for continuous variables. When performing descriptive analysis of categorical data, numbers and percentages will be provided for dichotomous and polychotomous variables. Bivariate comparisons of baseline characteristics and outcomes measures will be provided. Appropriate tests (eg, t-test, chi-square test) will be used based on the distributions of the measures. The cumulative incidence rate for clinical outcomes (major bleeding, stroke/SE, and death) will be calculated. The incidence rate will be calculated as the number of patients who experience the event divided by the observed time at risk. An unadjusted Kaplan-Meier curve will be drawn to illustrate time-to-event. The sample size of each cohort will be evaluated before proceeding with multivariate analysis.

The secondary objectives are optional, depending on the sample sizes and results from the primary objectives. For example, given the potential differences between ever-treated and never-treated with OAC patients, should the predictors/confounders from the primary objective be considered profound for the comparisons between the cohorts, objectives 2-5 will not be conducted.

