For the primary and secondary objectives, the first AF diagnosis date during the identification period will be used as the index date for both ever-treated and never-treated cohorts. Across both ever-treated and never-treated cohorts, all patients will be required to have a  $CHA_2DS_2$ -VASc $\geq 2$  and 12-months of continuous health plan enrollment, with medical and pharmacy benefits before the index date (baseline period). For the primary objective and high-risk subgroup analyses, patients will also be required to have 6-month continuous health plan enrollment, with medical and pharmacy benefits after the index date.

For the primary objective and high-risk subgroup analyses, the following patients will be excluded: an AF diagnosis any time prior to the first AF diagnosis; medical claims indicating a diagnosis or procedure for mitral valvular heart disease or heart valve replacement/transplant;

Do not distribute for purposes outside of specific activities related to development of FDAMAs114 compliant pieces. Content within this protocol is subject to change based on communication planning and input by external review committees.

Apixaban NON-INTERVENTIONAL STUDY PROTOCOL

or use of OACs during the baseline period. For the secondary objective assessing effectiveness, safety, and cost outcomes, patients will be further excluded if they had any of the following: venous thromboembolism; transient AF during the baseline period; pregnancy during the study period; hip/knee replacement surgery within 6 weeks pre-index date; or follow-up period = 0 day. In addition, among patients ever treated with an OAC, those with >1 OAC prescription claim at the index date will be excluded as well.

**Variables:** Baseline demographic and clinical characteristics will include age, gender, race, geographic region, Medicaid dual eligibility, Part-D low income subsidy, Charlson comorbidity index (CCI), CHADS2, CHA2DS2-VASc, HAS-BLED scores, prior bleeding/stroke events, congestive heart failure, diabetes, hypertension, chronic obstructive pulmonary disease, renal disease, myocardial infarction, dyspepsia or stomach discomfort, peripheral arterial disease, transient ischemic attack, coronary artery disease, history of falls, medication use, and index dose of DOAC. Baseline all-cause health care costs and utilization will be included.

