# 8.2.3. Cohorts

Patients eligible according to the above criteria will be assigned to the following cohorts:

Do not distribute for purposes outside of specific activities related to development of FDAMAs114 compliant pieces. Content within this protocol is subject to change based on communication planning and input by external review committees.

Apixaban NON-INTERVENTIONAL STUDY PROTOCOL

- 1) Ever-Treated Cohort: NVAF Patients had ≥1 pharmacy claim for apixaban, dabigatran, edoxaban, rivaroxaban, or warfarin from 01JAN2013-31DEC2016 on or after the first AF diagnosis
  - a. Apixaban cohort: Patients who initiated with apixaban on or after index date
  - b. Dabigatran cohort: Patients who initiated with dabigatran on or after index date
  - c. **Edoxaban cohort:** Patients who initiated with edoxaban on or after index date. Given the small sample size, edoxaban patients will not be included in the secondary clinical and healthcare utilization and costs analyses.
  - d. Rivaroxaban cohort: Patients who initiated with rivaroxaban on or after index date
  - e. Warfarin cohort: Patients who initiated with warfarin on or after index date
- 2) Never-Treated Cohort: NVAF patients with no pharmacy claim for an OAC from 01JAN2013-31DEC2016

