#### Apixaban

Table 2. Clinical and Treatment Pattern Outcome Variables					
Variable	Role	Operational Definition			
Stroke/SE	Outcome	Stroke/SE will be identified using hospital claims with a stroke/SE diagnosis code as the first listed ICD-9-CM or ICD-10-CM code. Stroke/SE will be classified into 3 categories: ischemic stroke, hemorrhage stroke, and SE. Time to stroke/SE will be defined as the number of days from index date to the occurrence of the first stroke/SE requiring hospitalization.			
Major bleeding	Outcome	Major bleeding will be identified using hospital claims with a bleeding diagnosis code as the first listed ICD-9-C or ICD-10-CM diagnosis or procedure code.  Time to major bleeding will be defined as the number of days from index date to the occurrence of the first major bleeding event requiring hospitalization. Major bleeding may be further stratified by gastrointestinal and intracranial hemorrhages and other major bleeding.			
Death	Outcome	Death information from the database will be used. Time to death will be defined as the number of days from index date to death.			
Discontinuation (Treated Patients)	Outcome	Treated patients will be considered to have discontinued if there was no additional refill for the index anticoagulant after 30 days of the previous prescription's run-out date.  The discontinuation date will be defined as the run-out date plus 30 days.			
Time to discontinuation (Treated Patients)	Outcome	Time to discontinuation will be defined as the number of days from the OAC prescription index date to the discontinuation date.			
Switch among anticoagulants (Treated Patients)	Outcome	A switch among anticoagulants will be defined as a prescription filled for non-index anticoagulants within 30 days before or after the run-out date.  Time to switch will be defined as the number of days from the OAC prescription index date to the first prescription date of the switch.			
Time-to-switch (Treated Patients)	Outcome	Time to switch will be defined as the number of days from the OAC prescription index date to the switch date.			

Table 2, Clinic	cal and Treatment Patt	ern Outcome Variables
	cal and frequencine i acc	

Do not distribute for purposes outside of specific activities related to development of FDAMAs114 compliant pieces. Content within this protocol is subject to change based on communication planning and input by external review committees.

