# 8.8. Subgroup and Sensitivity Analysis

Additional subgroup and sensitivity analyses will be conducted, including:

- high-risk CHA2DS2-VASc score subgroups, specifically, 2-3, 4-5, and ≥6 (primary objective): assess whether the predictors of treatment would be impacted by baseline CHA2DS2-VASc score.
- high-risk age subgroups, specifically, 65-74, 75-79, and  $\geq$ 80 years (primary objective): assess whether the predictors of treatment would be impacted by age.
- censor patients at 6 months (secondary clinical objectives): assess whether the differential follow-up time in each cohort would affect the clinical outcomes.
- use a certain allowable gap for drug exposure, such as 14 days (secondary clinical objectives): assess whether the allowable gap in OAC days of supply for treated patients would have an impact on the clinical outcomes, since a shorter allowable gap will increase the likelihood of having the patients truly on treatment.
- multivariable Cox regression (secondary clinical objectives): assess whether statistical methods on the multivariable analysis would affect the clinical outcomes.
- adjusting for the competing risks of death (secondary clinical objectives): assess whether death is a competing risk in the clinical outcome analyses.

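### Section 8.7 plans unadjusted outcome comparisons, rates and Kaplan-Meier curves with no split by treatment status; if grouped by ever/never cohort, death results carry immortal time bias, and the Kaplan-Meier complement overstates stroke/SE and bleeding risk

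*Protocol*

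**What the plan says.** **Time zero.** The Abstract states that "the first AF diagnosis date during the identification period will be used as the index date for both ever-treated and never-treated cohorts". Table 2 in Section 8.3 counts from that date: "Time to stroke/SE will be defined as the number of days from index date to the occurrence of the first stroke/SE requiring hospitalization" and "Time to death will be defined as the number of days from index date to death". Major bleeding is timed in the same way.

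**Cohorts.** Section 8.2.3 assigns patients by what happens after time zero. The apixaban cohort, for example, is "Patients who initiated with apixaban on or after index date". Any claim up to the end of 2016 makes a patient ever-treated; never-treated means no claim in 2013-2016. Section 8.2 follows treated patients from the index date, so the days before the first fill lie inside their follow-up.

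**Descriptive outputs.** Section 8.7 plans bivariate comparisons of outcome measures with tests such as the t-test and chi-square, and a cumulative incidence for each of the three clinical outcomes. Its rule for rates is: "The incidence rate will be calculated as the number of patients who experience the event divided by the observed time at risk". For the display over time, the section says only that "An unadjusted Kaplan-Meier curve will be drawn to illustrate time-to-event". It gives no grouping, time split or landmark, and no estimator for the cumulative incidence.

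**Comparative model.** For the secondary outcome objectives, the Abstract makes treatment status time-varying and credits an ever-treated patient's time off treatment to the untreated side. The Cox model in Section 8.7 does the same.

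**Competing death.** Section 8.8 lists, among the sensitivity analyses, "adjusting for the competing risks of death (secondary clinical objectives").

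**The concern.** An ever-treated patient must survive to the first fill. If curves and rates are drawn by ever/never cohort from AF diagnosis, those guaranteed-alive days enter the treated denominator. Patients who die before they would have started treatment are counted as never-treated. The treated cohort then looks better on death even when treatment does nothing.

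The protocol recognises this problem for the Cox model but gives the descriptive outputs no matching protection. A t-test or chi-square test needs each patient in one fixed group, and an ordinary Kaplan-Meier curve does not handle a group that changes over time. The named tools therefore do not fit the exposure definition used for the same objectives.

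The second issue is separate. Kaplan-Meier for stroke/SE or major bleeding treats death as censoring, so its complement exceeds the actual risk in a population where death is common.

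What is at stake is a descriptive report, due 7/1/2019, that could conflict with the multivariate results due 10/1/2019.

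**Working it through.** The plan states no figure on this point, so there is none to reproduce. The protocol gives no delay to treatment and no death rate. Both are assumed below and shown as ranges.

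**1. Death, ever versus never from index, no treatment effect.**

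Inputs: accrual uniform over 4 years with follow-up to the end of study (Sections 8.1 and 8.5). Assumed: half of patients are potential initiators, delay to the first fill is exponential, death rate is constant, and there is no censoring at discontinuation or switch. Each setting simulates 2,000,000 patients. Rate = deaths / person-years. Results for death at 10% per year, per 100 person-years:

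| Mean delay | Ever | Never | Ratio |
|---|---|---|---|
| 1 month | 9.51 | 10.44 | 0.91 |
| 3 months | 8.80 | 11.16 | 0.79 |
| 6 months | 7.90 | 11.87 | 0.67 |
| 12 months | 6.94 | 12.32 | 0.56 |

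At death rates of 5% and 15% per year the ratios move little: 0.92 and 0.92 at 1 month, 0.57 and 0.56 at 12 months. Splitting each patient's time at the first fill gives 0.99 to 1.01 in every setting. With a 6-month delay and 10% per year, for example, it gives 9.94 on treatment against 9.99 off treatment.

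A second pattern uses a monthly grid with entry spread over 48 months, death at 1 to 2% per month, and each month's starts counted before its deaths. Initiation at 10% per month for 3 months and 2% after gives a null hazard ratio of 0.53 to 0.55. Initiation at 25% per month for 2 months and 1% after gives 0.74 to 0.75. The lower end depends somewhat on the grid: counting deaths before starts lowers it further.

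**2. Stroke/SE under the same cohorts.**

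Under Section 8.2.3 a patient can have a stroke, start treatment afterwards, and still be ever-treated. The days before the fill are therefore not event-free by construction. With stroke at 3.7% per year (Section 8.5) and initiation independent of stroke, the null ratio is 0.99 to 1.01. Only if treatment had to start before the first event would it fall, to 0.55 to 0.91. In practice a stroke may prompt treatment and a bleed may deter it, so misclassified time could push the ratio either way.

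**3. Kaplan-Meier against cumulative incidence at 4 years.**

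With constant event rate s and death rate d:

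- Kaplan-Meier complement: 1 - exp(-4s)
- cumulative incidence: s/(s+d) × [1 - exp(-4(s+d))]

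For s = 0.037 the first is 1 - exp(-0.148) = 13.8%. For d = 0.10 the second is 0.037/0.137 × [1 - exp(-0.548)] = 11.4%.

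| s per year | d per year (assumed) | 1 - KM | Cumulative incidence | Ratio |
|---|---|---|---|---|
| 3.7% | 5% | 13.8% | 12.5% | 1.10 |
| 3.7% | 10% | 13.8% | 11.4% | 1.21 |
| 3.7% | 15% | 13.8% | 10.4% | 1.32 |
| 1.6% | 5% | 6.2% | 5.6% | 1.10 |
| 1.6% | 10% | 6.2% | 5.1% | 1.21 |
| 1.6% | 15% | 6.2% | 4.7% | 1.33 |

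The two values of s are the trial stroke/SE rates quoted in Section 8.5.

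**The case against.** The strongest reply is that the disputed analysis is not stated. Section 8.7 names no grouping. The Abstract makes treatment time-varying for the secondary objectives, Section 7 lists those comparisons as treated versus untreated, and time at risk could mean split person-time. Figures 2 and 3 might settle the matter but are not shown, and a statistical analysis plan could specify the displays. This stands to the extent that the bias is conditional on the grouping. It does not remove the point, because the protocol itself fixes the time origin, the rate formula, the fixed-group tests and Kaplan-Meier, and these do not fit time-varying exposure. Section 8.7 also speaks of evaluating each cohort and of differences between ever- and never-treated patients.

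Three stronger readings are tempting, and the documents do not support them:

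- **All descriptive outcomes carry immortal time bias.** Strictly, only death does; stroke/SE and bleeding can precede the first fill in an ever-treated patient.
- **The plan ignores competing death.** Section 8.8 plans a sensitivity analysis for it. Events over person-time ending at death is a valid cause-specific rate, and death as an outcome has no competing death. Section 8.7 also does not say that cumulative incidence will be taken from Kaplan-Meier.
- **The treatment comparison is biased in this way.** The time-varying Cox model credits time before treatment to the untreated side.

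It is also fair that the curves are labelled as unadjusted illustration, and that Section 8.7 makes the secondary objectives optional.

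**Conclusion.** The concern holds in a limited, conditional form. Section 8.7 does not align its unadjusted outcome comparisons, rates and curves with the time-varying treatment definition used elsewhere in the protocol. Produced by the Section 8.2.3 cohorts from AF diagnosis, which is the natural but unstated reading, the death results would show a null ratio of about 0.53 to 0.92. That range rests on assumed delays to treatment, death rates and initiation patterns. A reader might infer that a large spurious benefit is certain, but with a mean delay of one month the ratio is only about 0.91 to 0.92. For stroke/SE and bleeding the problem is misclassified exposure time of unknown direction.

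The Kaplan-Meier point does not depend on the grouping. Read as absolute risk, the curves for stroke/SE and bleeding overstate it; at the stroke/SE rates worked above, the factor at 4 years is about 1.1 to 1.3 for death at 5 to 15% per year. The sensitivity analysis in Section 8.8 does not alter the curve planned in Section 8.7.

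The weighted Cox estimates stand apart from both problems. The change is worth making, but it concerns descriptive output only.

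**What to change.** In Section 8.7, state that:

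- unadjusted incidence rates use treated and untreated person-time, with each event assigned to the treatment status at the time of the event;
- unadjusted curves use time-updated treatment (Simon-Makuch type) or start from a stated landmark, with status fixed at the landmark;
- cumulative incidence of stroke/SE and major bleeding uses the Aalen-Johansen estimator with death as a competing event, in place of the Kaplan-Meier complement; Kaplan-Meier remains suitable for death;
- outcomes are not tabulated, tested or plotted by ever/never cohort from the index date. That split stays with the predictor analysis of the primary objective.

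The cost is a few sentences in Section 8.7 and some added output. The time-varying Cox model already needs the person-time files, and no new data or change to the comparative analysis is required.

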# Logistic Regression: Predictors for OAC Treatment/non-treatment (Primary Objectives)

A logistic regression will be used to examine risk factors associated with OAC treatment (OAC, DOAC, or warfarin)/non-treatment with OACs and DOAC treatment/warfarin treatment. Predictor data will be examined during the 12 months baseline period before the index date.

Stepwise model selection will be used to identify risk factors. The final covariate lists will be finalized based on clinical rationale and model fitting.

Odds ratios, p-values, and 95% confidence intervals (CIs) for all model covariates will be provided. Diagnostic tests will be performed for the multivariate models. Hosmer-Lemeshow tests will be performed and the area under the Receiver Operating Characteristic curve will be checked.

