# 1. LIST OF ABBREVIATIONS

Abbreviation	Definition
AE	Adverse Event
AF	Atrial Fibrillation
CAD	Coronary Artery Disease
CCI	Charlson Comorbidity Index
CHADS 2	Congestive heart failure, Hypertension, Age ≥75 years, Diabetes mellitus, Stroke
CHA 2 DS 2 - VASc	Congestive heart failure, Hypertension, Age ≥75 years, Diabetes mellitus, Stroke, Vascular disease, Age 65-74 years, Sex category
CHF	Congestive Heart Failure
CI	Confidence Interval
CMS	Centers for Medicare & Medicaid Service
СРІ	Consumer Price Index
DME	Durable Medical Equipment
DOACs	Direct Oral Anticoagulants
ER	Emergency Room
FFS	Fee-For-Service
HAS-BLED	Hypertension, Abnormal renal/liver function, Stroke, Bleeding history or predisposition, Labile international normalized ratios, Elderly, Drugs/alcohol

Do not distribute for purposes outside of specific activities related to development of FDAMAs114 compliant pieces. Content within this protocol is subject to change based on communication planning and input by external review committees.

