#### Apixaban

NON-INTERVENTIONAL	STUDY DDOTOCOL
NON-INTERVENTIONAL	STUDIIKUIUCUL

Variable a	Role	Operational definition	
Index year	Baseline characteristic and potential predictor	A flag will be created for patients with index date in the year of 2013-2016.	
Medicaid dual eligibility	Baseline characteristic and potential predictor	A flag will be created for patients with Medicaid dual eligibility.	
Part-D low income subsidy	Baseline characteristic and potential predictor	A flag will be created for patients with a Part-D low income subsidy.	
Baseline Deyo-Charlson comorbidity index score	Baseline characteristic and potential predictor	The Deyo-Charlson comorbidity index score will be created during the baseline.	
Baseline CHADS2 score	Baseline characteristic and potential predictor	The CHADS 2 score will be used to analyze the effect of stroke risk stratification on OAC use. The maximum score is 6. CHADS 2 scores: 2-3, 4-5, and $\geq 6$ .	
Baseline CHA2DS2-VASc score	Baseline characteristic and potential predictor	The CHADS 2 VASc score will also be used as indicated above. The maximum score is 9. CHADS 2 -VASc scores: 2-3, 4-5, and $\geq 6$ .	
HAS-BLED score	Baseline characteristic and potential predictor	The HAS-BLED score will be used to estimate the risk of major bleeding. As the INR value is not available in the databases, a modified HAS-BLED score was calculated with a range of 0 to 8.	
Baseline prior bleed	Baseline characteristic and potential predictor	A flag will be created for patients with a bleeding- related claim during the baseline period.	
Baseline prior stroke/SE	Baseline characteristic and potential predictor	A flag will be created for patients with a stroke/SE claim during the baseline period.	
Obesity	Baseline characteristic and potential predictor	A flag will be created for patients with obesity claims during the baseline.	

Do not distribute for purposes outside of specific activities related to development of FDAMAs114 compliant pieces. Content within this protocol is subject to change based on communication planning and input by external review committees.

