#### Apixaban

NON-INTERVENTIONAL STUDY PROTOCOL

Variable a	Role	Operational definition		
Congestive heart failure	Baseline characteristic and potential predictor	A flag will be created for patients with claims for congestive heart failure during the baseline period.		
Diabetes	Baseline characteristic and potential predictor	A flag will be created for patients with claims for diabetes in the baseline period.		
Hypertension	Baseline characteristic and potential predictor	A flag will be created for patients with claims for hypertension in the baseline period.		
Chronic Obstructive Pulmonary Disease (COPD)	Baseline characteristic and potential confounder	A flag will be created for patients with COPD claims during the baseline		
Renal disease	Baseline characteristic and potential predictor	A flag will be created for patients with claims for renal disease in the baseline period.		
Myocardial infarction	Baseline characteristic and potential predictor	A flag will be created for patients with claims for myocardial infarction in the baseline period.		
Dyspepsia or stomach discomfort	Baseline characteristic and potential predictor	A flag will be created for patients with claims for dyspepsia or stomach discomfort in the baseline period.		
Peripheral arterial disease	Baseline characteristic and potential predictor	A flag will be created for patients with claims for peripheral arterial disease in the baseline period.		
Transient ischemic attack	Baseline characteristic and potential predictor	A flag will be created for patients with claims for transient ischemic attack in the baseline period.		
Coronary artery disease Baseline characteristic		A flag will be created for patients with claims for coronary artery disease in the baseline period.		

Do not distribute for purposes outside of specific activities related to development of FDAMAs114 compliant pieces. Content within this protocol is subject to change based on communication planning and input by external review committees.

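### CHADS2 is banded with no stratum for scores 0 and 1, which eligible patients can have, and the stepwise primary model lists risk scores beside their own components with no rule to keep them apart

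*Protocol*

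**What the plan says.** Section 8.7 (Logistic Regression, Primary Objectives) says "Stepwise model selection will be used to identify risk factors" and then "The final covariate lists will be finalized based on clinical rationale and model fitting". The output is fixed: "Odds ratios, p-values, and 95% confidence intervals (CIs) for all model covariates will be provided".

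Table 1 in Section 8.3 defines the candidates. CHADS2 is to be used for the effect of "stroke risk stratification on OAC use. The maximum score is 6", with bands 2-3, 4-5 and 6 or more. CHA2DS2-VASc has the same three bands and a maximum of 9. HAS-BLED and the Charlson index are also listed as baseline characteristics and potential predictors. The same role goes to age, sex, prior bleed, prior stroke/SE, heart failure ("A flag will be created for patients with claims for congestive heart failure during the baseline period"), hypertension, diabetes, renal disease, myocardial infarction and peripheral arterial disease.

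Section 8.2.1.1 requires age 65 or over and CHA2DS2-VASc of at least 2. It sets no CHADS2 minimum. Section 7 lists four contrasts for the primary objective. Section 8.8 adds three CHA2DS2-VASc and three age subgroups, the latter to "assess whether the predictors of treatment would be impacted by age".

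**The concern.** There are two separate problems.

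- **Banding.** The CHADS2 bands would suit a population selected on CHADS2 of at least 2. This one is selected on a different score, which gives points for age 65-74, sex and vascular disease. Some eligible patients therefore belong to no CHADS2 stratum, either in the baseline table or in a banded predictor.
- **Redundant candidates.** The stepwise search runs over composite scores and the items that make them up. Once a score is in the model, an item's odds ratio compares patients at the same score, so it no longer describes the item's own association. Conventional p-values and intervals also take no account of the selection.

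The odds ratios are the main product of the primary objective. Section 8.7 also makes secondary objectives 2-5 depend on how large the differences in predictors look.

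**Working it through.** **Inputs.** The items come from the abbreviation list: "Congestive heart failure, Hypertension, Age ≥75 years, Diabetes mellitus, Stroke" for CHADS2, with CHA2DS2-VASc adding the last three of "Stroke, Vascular disease, Age 65-74 years, Sex category". Weights follow from the subscripts. The age and score criteria are in Section 8.2.1.1, and the bands and maxima in Table 1.

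Write C, H, D, S, V and F as 0/1 indicators for heart failure, hypertension, diabetes, stroke, vascular disease and female sex, and A for age 75 or over.

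**1. Stated maxima.** CHADS2 = C + H + A + D + 2S, maximum 1+1+1+1+2 = 6. CHA2DS2-VASc maximum = 1+1+2+1+2+1+1 = 9. Both agree with Table 1.

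**2. Relation between the scores at age 65 or over.** CHA2DS2-VASc = C + H + 2A + D + 2S + V + (1 - A) + F = 1 + CHADS2 + V + F. CHADS2 is thus always 1 to 3 points lower, and the entry rule reduces to CHADS2 + V + F of at least 1. Examples:
- Woman aged 65-74, no other factor: CHA2DS2-VASc 2, CHADS2 0.
- Man aged 65-74 with hypertension: 2 and 1.
- Man aged 75 or over, no other factor: 2 and 1.

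**3. All profiles.** Seven binary items give 128 profiles, of which 127 are eligible. CHADS2 is distributed as follows:

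| CHADS2 | 0 | 1 | 2 | 3 | 4 | 5 | 6 |
|---|---|---|---|---|---|---|---|
| Profiles | 3 | 16 | 28 | 32 | 28 | 16 | 4 |

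So 3 + 16 = 19 profiles have no band and 108 are classified. The lowest CHA2DS2-VASc subgroup (2-3) has 6 + 16 = 22 profiles, of which 6 + 9 = 15 have CHADS2 0 or 1.

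**4. Share of patients.** The protocol gives no prevalences. Those below are assumptions, with items taken as independent.

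| Assumed setting | C | H | A | D | S | V | F | CHADS2 0-1 | CHADS2 = 6 |
|---|---|---|---|---|---|---|---|---|---|
| Healthier | .12 | .65 | .50 | .25 | .06 | .20 | .50 | 44.6% | 0.06% |
| Middle | .25 | .80 | .60 | .33 | .12 | .30 | .52 | 25.0% | 0.5% |
| Sicker | .40 | .90 | .70 | .40 | .20 | .40 | .55 | 11.6% | 2.0% |

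Middle row in full:
- P(CHADS2 = 0) = .75 × .20 × .40 × .67 × .88 = .0354.
- The ineligible part (no V, not F) is .0354 × .70 × .48 = .0119, leaving .0235.
- P(CHADS2 = 1) = .0354 × (.25/.75 + .80/.20 + .60/.40 + .33/.67) = .2238.
- Share = (.0235 + .2238)/(1 - .0119) = 25.0%.

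**5. Collinearity.** By step 2 each score is a linear function of its items. An intercept, the five CHADS2 items and linear CHADS2 give 7 columns of rank 6. The CHA2DS2-VASc equivalent is 9 columns of rank 8. With both scores it is 10 columns of rank 8. This assumes that the flags are defined as in the scores. Where they differ, the redundancy is near rather than exact.

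**6. What a retained score does.** Suppose linear CHA2DS2-VASc is kept in place of the age flag. The score's coefficient is then the age coefficient, and an item worth w points is reported as (own OR)/(score OR)^w. In a simulation of 200,000 patients (middle prevalences, assumed effects; 197,678 eligible), the components-only model gave heart failure 0.91, stroke 1.23 and age 0.82. With the score replacing age:
- Heart failure: 0.91/0.82 = 1.11 (fitted 1.11, direction reversed).
- Stroke: 1.23/0.82² = 1.83 (fitted 1.82; the difference is rounding).

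With a banded CHA2DS2-VASc beside all items, the odds ratios barely moved (stroke 1.23 to 1.20), while the stroke standard error rose from 0.014 to 0.022.

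**The case against.** The stepwise sentence is followed at once by a review on clinical grounds and model fit, and diagnostics are planned. Stepwise selection may therefore be only a screen, with redundant terms removed by judgement. Table 1 assigns a role; nowhere does the protocol say that scores and components enter the same model. Coding within the model and the final covariate list are often left to the SAP. This stands in part: joint retention is possible, not certain. But the review sentence sets no rule against it, and the protocol itself fixes the candidate list, the selection method and the CHADS2 bands.

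Three stronger readings are tempting and not supported:

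- **That the odds ratios are distorted.** This depends on which terms survive and on coding. The reversal in step 6 needs a linear score with an item dropped; a banded score hardly moved the estimates.
- **That patients with CHADS2 0-1 fall out of the primary model.** The protocol has no deletion rule. They would be lost only if CHADS2 were used banded and unclassified scores were set to missing. They could equally become an unlisted reference group. When they were dropped in the simulation (25%), the component odds ratios were about unchanged.
- **That selection is rerun in every contrast and subgroup with different covariates.** Sections 8.7 and 8.8 do not say so. With a very large sample, selection error in p-values and intervals may also be small; nothing here quantifies it.

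**Conclusion.** The banding is wrong as written. Eligible patients can score CHADS2 0 or 1 and have no assigned stratum, and the top band can only mean 6. The profile count (19 of 127) follows from the protocol's own definitions. The patient share of about 12% to 45% rests on assumed, independent prevalences. The baseline table is affected even if CHADS2 never enters a model.

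The redundancy is a conditional risk. Scores and their components share one stepwise candidate pool. If a score and some of its items are both retained, the item odds ratios may lose their interpretation and can change direction, and the reported p-values and intervals ignore the selection. The simulated sizes illustrate the mechanism under assumed effects and do not predict this study's results.

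**What to change.** - In Table 1, band CHADS2 as 0-1, 2-3, 4-6, or as 0-1, 2-3, 4-5, 6.
- In Section 8.7, prespecify a primary model with the components and no composite scores, and fit each score in its own separate model.
- Use the same covariate list across the four contrasts and, where a variable still varies, across the Section 8.8 subgroups.

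The cost is a line in Table 1, a short paragraph in Section 8.7 and a few more models. The primary model is less parsimonious, which matters little with the 100% Medicare database (Section 8.10).
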